#### 5.3.3.4.1 Selected laboratory parameters

Selected laboratory parameters will be graded according to CTCAE Version 4.03, the worst CTCAE grade will be summarized. All values will be considered, regardless of whether it is considered clinically significant or not.

For each test, subjects will be characterized based on their worst severity grade observed during on treatment period.

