2.2.1 Study Population

2.2.1.1 Inclusion Criteria

- 1) Histologically or cytologically confirmed unresectable or metastatic melanoma
- 2) Subjects with BRAF activating mutation must have received a BRAF inhibitor and/or MEK inhibitor regimen prior to study entry
- 3) Signed written informed consent approved by the relevant local ethics committee(s)
- 4) Male or female ≥ 18 years old at time of consent
- 5) Measurable disease by RECIST 1.1
 - a. For Cohort 3 only, subjects must have at least 3 measurable non-CNS target lesions
- 6) ECOG performance status of 0 or 1
- 7) Resolution of all disease or prior treatment-related toxicities to Grade ≤ 1 , with the exception of alopecia, Grade 2 neuropathy and laboratory abnormalities (parameters below apply). If subject received major surgery or radiation therapy of >30 Gy, they must have recovered from the toxicity and/or complications from the intervention
- 8) Adequate organ function within 14 days prior to first dose of investigational therapy(ies):
 - a. WBC $\geq 2 \times 10^9/L$ in absence of growth factor support
 - b. ANC $\geq 1.0 \times 10^9/L$ in absence of growth factor support
 - c. Platelet count $\geq 100 \times 10^9/L$
 - d. Hemoglobin $\geq 9 \text{ g/dL}$
 - e. Serum creatinine $\leq 1.5 \text{ mg/dL}$
 - f. Calculated (using the formula of local laboratory) or measured creatinine clearance $\geq 60 \text{ mL/min}$

- g. AST and ALT $\leq 2.5 \times$ ULN
- h. Total bilirubin $\leq 1.5 \times$ ULN, or direct bilirubin \leq ULN for subjects with total bilirubin levels $> 1.5 \times$ ULN
- i. INR or PT $\leq 1.5 \times$ ULN unless subject is receiving anticoagulant therapy as long as PT or PTT is within therapeutic range of intended use of anticoagulants
- j. aPTT $\leq 1.5 \times$ ULN unless subject is receiving anticoagulant therapy as long as PT or PTT is within therapeutic range of intended use of anticoagulants

9) Women of childbearing potential (WOCBP) must have a negative serum pregnancy test within the 7 days prior to first dose of investigational therapy(ies) and a negative urine pregnancy test within the 3 days prior to first dose of investigational therapy(ies), or a negative serum pregnancy test within the 3 days prior to first dose of investigational therapy(ies)

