6.3 Endpoint Definitions

Endpoint	Description
Primary	
• ORR (rate of CR and PR) by RECIST 1.1 in each cohort
Secondary	
• Incidence and severity of AEs and specific laboratory abnormalities graded according to NCI-CTCAE, v4.03• Changes from baseline of vital signs and clinical laboratory results during and following investigational therapy(ies) administration• ORR (rate of CR and PR) by iRECIST in each cohort• DOR (by RECIST 1.1) by cohort, defined as the time from the first evidence of confirmed PR or better to disease progression or death due to any cause• DOR (by iRECIST) by cohort, defined as the time from the first evidence of confirmed PR or better to disease progression or death due to any cause
Exploratory	
• PFS (by RECIST 1.1) by cohort, defined as time from first dose of investigational therapy(ies) to the earlier of PD or death due to any cause• PFS (by iRECIST) by cohort, defined as time from first dose of investigational therapy(ies) to the earlier of PD or death due to any cause• Association between potential tumor and/or blood biomarkers and antitumor activity and/or resistance to treatment• Presence and titer of anti-APX005M antibodies

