**Table 2 Time unit conversion factors**

1 week	7 days
1 month	30.4375 days
1 year	365.25 days

**Study day:** The date on which the first dose of APX005M is administered is considered as Day 1 of the study.

For the events occurring on or after this day, the study day is calculated as the event date minus the date of the first administration of APX005M plus 1 day.

For the events occurring before the start of treatment, study day is calculated as the event date minus the date of the first administration of APX005M.

**Baseline:** is defined as the last non-missing value before treatment.

**On treatment period** is defined as the time elapsed (in months) from the first dose of APX005M and the date of End of Treatment reported at the End of Treatment form.

**Follow up period** is defined as the time elapsed (in months) from the date of the End of Treatment reported at the End of Treatment form and the date of the End of the Study reported at the End of the Study form.

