### 5.3.3.4 Clinical Laboratory Evaluation

To evaluate the safety profile the following laboratory tests will be performed locally:

- Serum chemistry
- Hematology
- Coagulation
- Urinalysis
- Pregnancy.

For each quantitative laboratory parameter, the values, and changes from baseline will be summarized (including number, mean, SD, median, Q1, Q3, minimum, and maximum) will be calculated for each visit or study assessment by cohort.

The frequency of subjects with clinically significant abnormal laboratory values will be tabulated for baseline and each scheduled post baseline visit, by cohort and overall.

The shift tables for baseline versus all visits will be presented for all chemistry and hematology laboratory parameters based on categories of below, within and above normal range.

Lab Original results with ND/ NA/ NE/ UNK/ NQ/ UN etc: will not be evaluated or used for the analysis purpose.

All serum chemistry, hematology, coagulation, and urinalysis data will be listed by subject; the clinically significant abnormal values will be flagged.

Notes:

- Clinical laboratory data will be analysed using standardized values.
- Repeated or unscheduled tests will not be summarized for each scheduled visit but will be included in the listing.
- The tables will include the visits until the number of patients will be representative.
- Only evaluable data will be used, and missing data will not be imputed.

The pregnancy results will also be listed only.

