**Table 8 Grading of selected laboratory parameters - Hematology**

Laboratory abnormality	CTCA V4.03 Term	Grade 1	Grade 2	Grade 3	Grade 4
Leukocytes (Low)	White Blood Cells decreased	<LLN-3000/mm3; <LLN-3.0x10e9/L	<3000-2000/mm3; <3.0-2.0x10e9/	<2000-1000/mm3; <2.0-1.0x10e9/L	<1000/mm3; <1.0x10e9/L
Neutrophil (Low)	Neutrophil count decreased	<LLN-1500/mm3; <LLN-1.5 x 10e9/L	<1500-1000/mm3; <1.5-1.0 x10e9/L	<1000-500/mm3; <1.0-0.5x10e9/L	<500/mm3; <0.5x10e9/L
Platelet (Low)	Platelet count decreased	<LLN-75000/mm3; <LLN-75.0x10e9/L	<75000- 50000/mm3; <75.0-50.0x10e9/L	<50000- 25000/mm3; <50.0- 25.0x10e9/L	<25000/mm3; <25.0x10e9/L
Lymphocyte (Low)	Lymphocyte count decreased	<LLN-800/mm3; <LLN-0.8 x10e9/L	<800-500/mm3; <0.8-0.5 x10e9/L	<500-200/mm3; <0.5-0.2x10e9/L	<200/mm3; <0.2x10e9/L
Hemoglobin (Low)	Anemia	<LLN - 10.0 g/dL; <LLN- 6.2 mmol/L; <LLN - 100 g/L	<10.0 - 8.0 g/dL; <6.2 - 4.9 mmol/L; <100 - 80g/L	<8.0 g/dL; <4.9 mmol/L; <80 g/L;	—
White Blood Cells (High)	Leukocytosis	—	—	> 100000/mm3;	—
Lymphocyte (High)	Lymphocyte count increased	—	>4000- 20000/mm3	>20000/mm3;	—

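### Laboratory abnormalities are reported as worst on-treatment CTCAE grade without the baseline grade, although eligible subjects can enter at Grade 2 or higher on several of the graded tests

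*SAP*

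**What the plan says.** Protocol 6.3 makes this a secondary safety endpoint: "Incidence and severity of AEs and specific laboratory abnormalities graded according to NCI-CTCAE, v4.03". A separate secondary endpoint in the same table is change from baseline in clinical laboratory results.

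SAP 5.3.3.4.1 implements the graded part. For each test, "subjects will be characterized based on their worst severity grade observed during on treatment period", and "All values will be considered, regardless of whether it is considered clinically significant or not". The notes for both panels add that repeated and unscheduled tests count. Tables 8 and 9 give the bands for 11 graded abnormalities, 7 in hematology and 4 in serum chemistry.

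SAP 4.1 has the definitions that a baseline comparison would need. Baseline "is defined as the last non-missing value before treatment", and the on-treatment period is "the time elapsed (in months) from the first dose of APX005M and the date of End of Treatment". The grade tables use the second definition and not the first.

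SAP 5.3.3.4 uses baseline in other displays: change from baseline by visit, clinically significant abnormal values at baseline and at each scheduled visit, and chemistry and hematology shift tables "based on categories of below, within and above normal range". All values are also listed by subject.

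Protocol 2.2.1.1, criterion 7, exempts laboratory abnormalities from the rule that earlier toxicities must have resolved to Grade 1 or less. The limits in criterion 8 apply instead, for example "ANC $\geq 1.0 \times 10^9/L$ in absence of growth factor support".

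**The concern.** The ANC limit shows the problem. The lowest value allowed at entry lies in the SAP's own Grade 2 band for neutrophils, "<1500-1000/mm3; <1.5-1.0 x10e9/L". A subject who enters there and does not change has a worst on-treatment grade of 2. The table counts that subject exactly as it counts one whose neutrophils fell from normal to the same level.

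The cohorts have no untreated control, so no background rate is available to set against these counts. Each subject's own baseline is the natural reference. If it is left out, a secondary safety endpoint mixes what subjects brought into the study with what changed during treatment. Several affected tests bear on effects that Protocol 1.2.4 already describes for APX005M, namely falls in lymphocyte count and transient bilirubin increases.

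**Working it through.** The plan states no figure on this point, so there is none to reproduce. The check sets the entry limits against the grade bands.

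**Step 1: highest grade an eligible subject can carry in.** Limits are from Protocol 2.2.1.1, criterion 8. Bands are from SAP Tables 8 and 9.

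| Abnormality | Entry limit | Band reached | Highest grade at entry |
|---|---|---|---|
| WBC low | ≥2.0 ×10⁹/L | Grade 2: <3.0 to 2.0 | 2 |
| ANC low | ≥1.0 ×10⁹/L | Grade 2: <1.5 to 1.0 | 2 |
| Hemoglobin low | ≥9 g/dL | Grade 2: <10.0 to 8.0 | 2 |
| Total bilirubin | ≤1.5 × ULN; no cap on total if direct ≤ULN | Grade 2: >1.5 to 3.0 × ULN; Grade 3: >3.0 to 10.0 × ULN | 2 or higher |
| Lymphocytes, low or high | none | all bands | any |
| Alkaline phosphatase | none | all bands | any |
| Platelets low | ≥100 ×10⁹/L | Grade 1: <LLN to 75 | 1 |
| AST, ALT | ≤2.5 × ULN | Grade 1: >ULN to 3.0 × ULN | 1 |

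WBC increased is the remaining abnormality. Its only band in Table 8 is Grade 3, above 100,000/mm³. No entry limit rules it out, but it is not a plausible entry value.

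**Step 2: where carry-in is impossible.** Grade 3 starts below 2.0 for WBC, below 1.0 for ANC, below 8.0 g/dL for hemoglobin, below 50 for platelets, and above 5.0 × ULN for AST and ALT. All of these lie beyond the entry limits. For these six tests, a Grade 3 or higher on treatment is a worsening in any subject whose baseline met the limits. For platelets, AST and ALT the same holds from Grade 2 (below 75; above 3.0 × ULN).

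**Step 3: can the other summaries recover the change?** Compare two subjects:
- Hemoglobin 9.2 g/dL at entry, unchanged: Grade 2 to Grade 2.
- Hemoglobin 10.0 g/dL at entry, falling to 9.2: Grade 1 to Grade 2.

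Both appear as worst Grade 2 in the grade table. Both appear as below range to below range in the shift table. The same shift cell also holds an ANC that stays at 1.0 (Grade 2) and one that falls from 1.0 to under 0.5 (Grade 4). The shift table shows a move from normal to abnormal, but not a move between grades. The by-visit summaries leave out unscheduled tests, whereas the worst-grade table includes them. A worst value found at an unscheduled visit therefore has no baseline comparison in any summary that the SAP text describes.

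**Step 4: size.** One unchanged subject adds 1/n to the reported incidence. With the planned 11, 11 and 18 subjects, 1/11 = 9.1 points and 1/18 = 5.6 points.

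The documents give no baseline grade frequencies. As an illustration only, assume that a share q enters at Grade 2 or higher on one test, that those subjects stay unchanged, and that the drug has no effect. The expected count is n × q, and the chance of at least one such subject is 1 − (1 − q)ⁿ.

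| n | q = 5%: expected, P(≥1) | q = 30%: expected, P(≥1) |
|---|---|---|
| 11 | 0.6, 0.43 | 3.3, 0.98 |
| 18 | 0.9, 0.60 | 5.4, 0.998 |

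Under the same assumptions, a count of subjects who worsen by at least one grade would be 0.

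**The case against.** The strongest reply is that the SAP delivers what the protocol asks for. The endpoint is graded abnormalities, and a worst-grade table gives them. The SAP calls them abnormalities, not treatment-emergent or drug-related events. Attribution runs through adverse-event reporting, since Protocol 5.3.8 sends clinically significant or action-requiring laboratory findings there. Baseline is used in three neighboring displays, and with 11, 11 and 18 subjects the listings let a reader trace each subject. The table shells are in a separate document that is not available here and may already show baseline grade. The study is exploratory, and no decision rule depends on these counts.

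Much of this stands, and it rules out three stronger readings that a reader might infer:
- **That the laboratory toxicity profile as a whole is overstated.** Step 2 shows that the Grade 3 or higher counts for six tests cannot be inflated in eligible subjects, and without baseline frequencies the rest can only be called possibly inflated.
- **That Cohort 3 enters with worse values, so the cohorts are not comparable.** Cohort 3 allows any number of prior lines, but criterion 8 is the same for all cohorts and no document gives baseline laboratory data.
- **That the plan ignores baseline.** It does not; what is missing is baseline by CTCAE grade.

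The reply does not remove the core. The other displays do not use CTCAE grade, and reconstructing grade changes by hand from listings is not a planned summary.

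**Conclusion.** The point holds in limited form. As written, SAP 5.3.3.4.1 can count an unchanged entry abnormality as an on-treatment abnormality. This is possible at Grade 2 for low WBC, ANC and hemoglobin, at Grade 2 or higher for total bilirubin with direct bilirubin at or below ULN, and at any grade for lymphocytes and alkaline phosphatase. For platelets, AST and ALT it is confined to Grade 1.

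The size is unknown. The 9.1 and 5.6 points per subject assume safety populations of the planned size. Treated subjects who were not evaluable could be replaced, so the actual denominators may be larger and the steps smaller. The conclusion on Grade 3 or higher assumes that the baseline value itself met the entry limits; Protocol 4.1.2.1 has eligibility confirmed on Cycle 1 Day 1. The primary endpoint is not affected. The change is worth making because the endpoint is a stated secondary one, there is no untreated control, and the data are already collected.

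**What to change.** In SAP 5.3.3.4.1:

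1. Keep the worst-grade counts as they are.
2. For each test in Tables 8 and 9, add a by-cohort shift table of baseline CTCAE grade against worst on-treatment grade. Take baseline as the last value before first treatment, as in SAP 4.1, and include unscheduled tests in the worst grade.
3. From that table, report the number of subjects who worsen by at least one grade. Such a count misses worsening within a grade, which is one reason to show it beside the worst-grade counts and not in their place.
4. State that same-day pre-dose Cycle 1 Day 1 values are baseline and not on-treatment. The definitions in SAP 4.1 point that way, and the LDH subgroup in SAP 5.3.4.2 already treats Cycle 1 Day 1 as pre-treatment. However, the chemistry and hematology samples in Protocol 4.1.2.1 carry no pre-infusion label.

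If the external shells already contain such a table, the SAP text need only say so. The cost is a few lines of SAP text and one extra table per panel. No new samples or visits are needed, and the entry criteria stay as they are.

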### 5.3.3.4.1.1 *Hematology*

In hematology, a table with the following abnormalities of laboratory parameters will be described:

- White Blood Cells decreased
- Neutrophil count decreased
- Platelet count decreased
- Lymphocyte count decreased
- Hemoglobin decreased.
- White Blood Cells increased
- Lymphocyte count increased

**Note:**

Repeated or unscheduled tests will be considered in calculating this information.

**Table 8 Grading of selected laboratory parameters - Hematology**

Laboratory abnormality	CTCA V4.03 Term	Grade 1	Grade 2	Grade 3	Grade 4
Leukocytes (Low)	White Blood Cells decreased	<LLN-3000/mm3; <LLN-3.0x10e9/L	<3000-2000/mm3; <3.0-2.0x10e9/	<2000-1000/mm3; <2.0-1.0x10e9/L	<1000/mm3; <1.0x10e9/L
Neutrophil (Low)	Neutrophil count decreased	<LLN-1500/mm3; <LLN-1.5 x 10e9/L	<1500-1000/mm3; <1.5-1.0 x10e9/L	<1000-500/mm3; <1.0-0.5x10e9/L	<500/mm3; <0.5x10e9/L
Platelet (Low)	Platelet count decreased	<LLN-75000/mm3; <LLN-75.0x10e9/L	<75000- 50000/mm3; <75.0-50.0x10e9/L	<50000- 25000/mm3; <50.0- 25.0x10e9/L	<25000/mm3; <25.0x10e9/L
Lymphocyte (Low)	Lymphocyte count decreased	<LLN-800/mm3; <LLN-0.8 x10e9/L	<800-500/mm3; <0.8-0.5 x10e9/L	<500-200/mm3; <0.5-0.2x10e9/L	<200/mm3; <0.2x10e9/L
Hemoglobin (Low)	Anemia	<LLN - 10.0 g/dL; <LLN- 6.2 mmol/L; <LLN - 100 g/L	<10.0 - 8.0 g/dL; <6.2 - 4.9 mmol/L; <100 - 80g/L	<8.0 g/dL; <4.9 mmol/L; <80 g/L;	—
White Blood Cells (High)	Leukocytosis	—	—	> 100000/mm3;	—
Lymphocyte (High)	Lymphocyte count increased	—	>4000- 20000/mm3	>20000/mm3;	—

### 5.3.3.4.1.2 Serum chemistry

In serum chemistry, a table with the following abnormalities of laboratory parameters will be described:

- AST increased
- ALT increased
- Total bilirubin increased
- Alkaline phosphatase increased
- Concurrent (AST or ALT) and Total Bilirubin (Hy's law)

Note:

- Repeated or unscheduled tests will be considered in calculating this information.

**Table 9 Grading of selected laboratory parameters – Serum chemistry**

Laboratory abnormality	CTCA V4.03 Term	Grade 1	Grade 2	Grade 3	Grade 4
Aspartate Aminotransferase increased (High)	Aspartate Aminotransferase increased	>ULN - 3.0 x ULN	>3.0 - 5.0 x ULN	>5.0 - 20.0 x ULN	>20.0 x ULN
Alanine Aminotransferase increased (High)	Alanine Aminotransferase increased	>ULN - 3.0 x ULN	>3.0 - 5.0 x ULN	>5.0 - 20.0 x ULN	>20.0 x ULN
Total bilirubin (High)	Blood bilirubin Increased	>ULN - 1.5 x ULN	>1.5 - 3.0 x ULN	>3.0 - 10.0 x ULN	>10.0 x ULN
Alkaline Phosphatase increased (High)	Alkaline Phosphatase increased	>ULN - 2.5 x ULN	>2.5 - 5.0 x ULN	>5.0 - 20.0 x ULN	>20 x ULN

### Hy's law

Concurrent (AST or ALT) and Total Bilirubin.

- The number of subjects and events reported per cohort will be included
- eDISH plots will be provided. (Scatter plots of peak ALT/AST versus peak Total bilirubin in the same date)

### 5.3.3.5 Vital Signs

Vital sign measurements, including blood pressure (Systolic/Diastolic) (mmHg), Pulse Rate (beats/minute), Respiration Rate (breaths/min), and Temperature, will be performed at Screening, during and after the investigational product infusion within Treatment Phase, and at EOT.

All vital signs measurements will be listed by subject.

### 5.3.3.6 12-Lead Electrocardiogram (ECG)

12-lead ECG measurements will be conducted locally, including RR Interval (msec), PR interval (msec), QRS interval (msec), QT interval (msec).

ECG overall interpretation will also be collected on eCRF (Normal / Abnormal NCS / Abnormal CS).

The ECG measurements are required at Screening only; additional ECGs can be performed as clinically indicated.

All ECG measurements and overall interpretation results will be listed by subject.

### 5.3.3.7 Physical Examination

A physical examination (including examination of the skin, head and neck, chest (heart and lungs), abdomen, limbs, and a brief neurological examination) will be assessed at the Screening, Treatment Phase, and EOT.

Any clinically significant abnormality at Screening will be recorded on eCRF pages for medical history; any clinically significant abnormality at all other visits will be recorded on AE forms.

Data from examinations will be listed by subject.

### 5.3.3.8 ECOG Performance Status

The six-grade ECOG Performance Status will be recorded at Screening, Treatment Phase, and EOT.

All ECOG performance status data will be listed by subject.

## 5.3.4 Subgroup analysis

### 5.3.4.1 Steroids during treatment- Subgroup

For subjects receiving steroids for each dose of APX005M, the BOR will be provided. It will be summarized in different approaches:

- Subjects receiving steroids during treatment: For the first dose, the window should be from screening to 5 days after the first dose - all other cycles should be +/-5 days from the APX005M
- Subjects receiving steroids for the first dose: the window should be from screening to 5 days after the first dose of APX005M.

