2.2 Study Design and Duration

This is a multicenter, open label, Phase 2 study, with 3 parallel cohorts. The aim of the study is to evaluate the efficacy of:

- a) APX005M administered at 2 different schedules to adult subjects with unresectable or metastatic melanoma who have not received prior immunotherapy. Enrolled subjects will be alternately assigned to one of the following 2 cohorts as long as both cohorts are open:
Cohort 1: APX005M administered IV at 0.3 mg/kg every 3 weeks (21-day cycle)

Cohort 2: APX005M administered IV at 0.3 mg/kg every 2 weeks (14-day cycle)

The intent of the alternating cohort assignment is to maintain approximately the same number of treated subjects in each of these 2 cohorts at any given time. Therefore, enrolled subjects assigned to Cohorts 1 or 2 who do not receive APX005M or are not evaluable for tumor response (see below) will be replaced in that cohort before assigning new subjects to the other cohort.

- b) APX005M in combination with stereotactic body radiation therapy (SBRT) in adults with unresectable or metastatic melanoma who have failed approved immunotherapy regimens:

Cohort 3: APX005M administered IV at 0.3 mg/kg in combination with radiation therapy every 2 weeks (14-day cycle) up to 16 weeks followed by APX005M administered IV at 0.3 mg/kg every 2 weeks (14-day cycle).

[figure not shown]
Subjects enrolled in Cohort 3 are required to have a minimum of 3 non-central nervous system (CNS) measurable target lesions as defined in RECIST 1.1 (see [Section 3.2.2](#)). Subjects will receive APX005M combined with SBRT followed by single agent APX005M:

- Four cycles consisting of radiation (one fraction of 800 cGy per cycle delivered to the same target lesion) followed by systemic administration of APX005M every 2 weeks for a total period of 8 weeks.
- Tumor assessment
- Four additional cycles consisting of radiation (one fraction of 800 cGy per cycle delivered to one target lesion different from the one previously irradiated) followed by systemic administration of APX005M every 2 weeks for a total period of 8 weeks.
- Tumor assessment

- Single agent APX005M until any of the criteria in [Section 3.2.6.1](#) are met.

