### 2.2.4 Subgroup Analysis not included in the protocol

#### 2.2.4.1 Steroids during treatment- Subgroup

For subjects receiving steroids, the Best Overall Response (BOR) will be provided. We will consider two scenarios:

- Subjects receiving steroids during treatment. For the first dose, the window should be from screening to 5 days after the first dose - all other cycles should be +/- 5 days from the APX005M
- Subjects receiving steroids for the first dose. The window should be from screening to 5 days after the first dose.

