**Table 1 Analysis population**

	Efficacy	SAF	PP
DEMOGRAPHIC CHARACTERISTICS			
-Baseline characteristics	x	x	x
-Previous treatment	x		
EFFICACY (Primary & secondary endpoints)			
Primary endpoint: -ORR by RECIST in each cohort	x		x
Secondary endpoints: -Evaluate ORR by modified RECIST 1.1 for immune-based therapeutics (iRECIST) in each cohort -Evaluate median duration of response (DOR) by RECIST in each cohort	x		
SAFETY			
Secondary objective: -Evaluate the safety of APX005M alone or in combination with radiation therapy in each cohort -Treatment exposure		x	

	Efficacy	SAF	PP
Exploratory endpoints			
- PFS (by RECIST 1.1 and iRECIST) by cohort - Duration of stable disease by cohort.	x		
Subgroup analysis			
- Subjects receiving steroids during treatment period by cohort. - LDH pre-treatment values above the upper normal range vs. below upper normal range overall and by cohort - Elevated pre-treatment LDH and prior CTLA4 overall and by cohort	x		

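### Steroid status in the 'during treatment' subgroup accrues over the same period as BOR, so it depends on treatment duration; whether any or every dose qualifies is unsettled and sets the direction of the distortion

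*SAP*

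**What the plan says.** The SAP adds a steroid subgroup that is not in the protocol and describes it twice. SAP 2.2.4.1 opens with "For subjects receiving steroids, the Best Overall Response (BOR) will be provided"; SAP 5.3.4.1 opens with "For subjects receiving steroids for each dose of APX005M, the BOR will be provided". Both then give two versions.

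- *During treatment.* For the first dose, the window runs from screening to 5 days after that dose. After that, "all other cycles should be +/-5 days from the APX005M".
- *First dose only.* "Subjects receiving steroids for the first dose: the window should be from screening to 5 days after the first dose of APX005M".

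Table 1 of the SAP assigns the analysis to the efficacy population and labels it "Subjects receiving steroids during treatment period by cohort". Neither section sets a landmark or a cut-off at first response. Neither names a group without steroids.

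Three other provisions matter. BOR uses assessments up to the end of treatment or 30 days after the last dose (SAP 4.4.1.1). Progression normally ends treatment (Protocol 3.2.6.1), with treatment beyond progression as a permitted exception (Protocol 3.2.6.2). Otherwise treatment may run for up to 12 months (Protocol 3.2.1).

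**The concern.** Steroid status in the first version is built up during follow-up and then tabulated against an outcome from the same follow-up. A subject who progresses at the first scan has a handful of windows in which to be classified. A responder who stays on treatment has many more, and some of them fall after the response has been recorded. This is the usual time-dependent exposure (immortal-time) problem.

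The wording adds a second difficulty. Under an any-dose rule, each further cycle is another chance to qualify. Under an every-dose rule, which is the literal sense of the 5.3.4.1 sentence, each further cycle is another chance to fail. The two readings push the response rate among recipients in opposite directions, so two programmers could produce tables that point opposite ways from the same data.

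ORR is also reported for each cohort and overall (SAP 5.3.2.1). A reader can therefore set the recipients' BOR beside it and take the gap for a steroid effect.

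**Working it through.** **The plan's own figures.** Protocol 6.1 assumes 2/11 = 18.2% with standard error √(0.182 × 0.818 / 11) = 11.6%, and 3/18 = 16.7% with standard error √(0.167 × 0.833 / 18) = 8.8%. Both reproduce. Across all three cohorts the planning rate is (2 + 2 + 3)/(11 + 11 + 18) = 7/40 = 17.5%, used below as the true ORR unless stated.

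**Inputs from the documents.**
- Protocol 2.2 gives "Cohort 1: APX005M administered IV at 0.3 mg/kg every 3 weeks (21-day cycle") and "Cohort 2: APX005M administered IV at 0.3 mg/kg every 2 weeks (14-day cycle"); Cohort 3 is also on 14 days.
- A window of 5 days either side of a dose covers 11 days: 11/14 = 79% of a two-week cycle and 11/21 = 52% of a three-week cycle.
- By the first assessment at about week 8, 4 doses have been given on the two-week schedule and 3 on the three-week schedule.
- Confirming a response 4 weeks later takes a responder to about 7 or 5 doses respectively, counting the dose due at week 12. Twelve months allows about 26 or 18.

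**Assumed.** The documents give no steroid rate. Let *q* be the chance of steroids at each dose, independent of response (no steroid effect), and *k* the number of doses received.

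**Formulas.**
- Any dose: P(recipient) = 1 − (1 − *q*)^*k*
- Every dose: P(recipient) = *q*^*k*
- ORR in recipients = ORR × P(recipient | responder) ÷ [ORR × P(recipient | responder) + (1 − ORR) × P(recipient | non-responder)]

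**Main illustration, any dose, *q* = 10%, responders 12 cycles.**
- Responders: 1 − 0.9^12 = 0.718.
- Non-responders with 4 cycles: 1 − 0.9^4 = 0.344. ORR in recipients = 0.175 × 0.718 ÷ (0.175 × 0.718 + 0.825 × 0.344) = 0.1256/0.4093 = 31%.
- Non-responders with 8 cycles: 1 − 0.9^8 = 0.570. ORR in recipients = 0.1256/(0.1256 + 0.4698) = 21%.

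**Sensitivity to the assumptions.**

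| Rule | *q* per dose | Doses, responder / non-responder | True ORR | ORR in recipients |
|---|---|---|---|---|
| Any | 10% at doses 1–2, then 1% | 12 / 4 | 17.5% | 22% |
| Any | 5% | 7 / 4 | 16.7% | 24.5% |
| Any | 5% | 13 / 4 | 16.7% | 34% |
| Any | 5% | 26 / 4 | 16.7% | 44% |
| Every | 80% | 13 / 4 | 16.7% | 3% |
| Every | 95% | 13 / 4 | 16.7% | 11% |
| First dose only | 5%, 10% or 20% | 1 / 1 | 16.7% | 16.7% |

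The front-loaded row is 1 − 0.9² × 0.99^10 = 0.267 for responders against 1 − 0.9² × 0.99² = 0.206 for non-responders, so 0.0468/(0.0468 + 0.1701) = 22%.

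The last row shows that the artefact comes from the accruing window: one fixed window for everyone removes it in this model.

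**The case against.** A reader might infer that the table will make steroids look harmless or beneficial. The documents do not support that.

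- **Direction.** The every-dose reading reverses it. Under either reading, steroid use is unlikely to be independent of treatment duration. Several toxicities for which the protocol advises corticosteroids (3.2.3.2) also lead to discontinuation under its Table 3, and failure to taper corticosteroids is itself a reason to stop (3.2.6.1). Both pull recipients towards short treatment and could offset an upward bias.
- **Comparison.** A reader might also infer a planned contrast of recipients with non-recipients. The SAP promises BOR in recipients only. The LDH subgroup, by contrast, names two groups and lists ORR and DCR. Any steroid comparison is informal, against the whole cohort.
- **Purpose.** Nothing says the table is meant to show whether steroids blunt response. That is an inference from the eligibility and concomitant-therapy restrictions.
- **Size.** Four non-responder cycles is the unfavourable end. Non-responders include stable disease, and treatment beyond progression is allowed. Use may also cluster in the early cycles. Either change brings 31% down to about 21–22%.
- **Already covered in part.** The first-dose version sits in the same section, and concomitant medications are listed by subject.

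All of these points stand as limits on direction, size and importance. None of them removes the structural dependence of steroid status on treatment duration, and the first-dose table does not correct the other one.

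**Conclusion.** The point holds as a defect of definition. Steroid status in the 'during treatment' table depends on treatment duration, exposure after a response counts, and the two SAP sections leave open whether any or every dose is required. With no steroid effect, the any-dose rule gives 31% or 21% in recipients (4 or 8 non-responder cycles) against 17.5% for all subjects. The every-dose rule can give 3% against 16.7%.

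These figures rest on an assumed steroid rate, fixed cycle counts and independence of steroids from response, so they illustrate the mechanism and do not predict the result. The net direction and size in the real data cannot be known from the documents. The analysis is a descriptive subgroup in cohorts of 11, 11 and 18, planned around two or three responders each, and no primary or secondary result depends on it. It should be corrected because the correction is cheap.

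**What to change.** 1. Use one definition in SAP 2.2.4.1 and 5.3.4.1: steroids at any dose within the stated window. Align the Table 1 label.
2. Make the existing first-dose window the main steroid table. It extends 5 days past dose 1, so it is not strictly baseline, but essentially every treated subject has it.
3. Restrict the 'during treatment' table to steroids given at doses before the first on-study tumor assessment (week 8 ± 1). Report BOR for subjects still on study at that assessment.
4. Show subjects who left earlier in a separate row by steroid status. The note in SAP 3.1 deliberately keeps early deaths and early clinical progressions in the efficacy population. A plain landmark would drop them and raise apparent response.
5. Label the table descriptive, with no causal reading, and leave later steroid use to the concomitant-medication listing (SAP 5.3.1.7).

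The cost is SAP wording, a date filter and one extra row, with no new data. The downside is that later steroid use is no longer tabulated and the cells are small.
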